5.1. Primary endpoint

The primary endpoint is leakage through coupling registered at each bag change. This is a yes/no response from the subject.

5.2. Secondary endpoints

The secondary endpoints are as follows:

- Product satisfaction evaluated at end of study by a question on a 4-point scale
- Preference evaluated at end of study by the question "Would you consider using the new coupling in the future? (Yes/No)"

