A follow-up call will be scheduled 7 ± 1 days after each test visit to ensure compliance with the provided product and study procedures. Additional calls may be scheduled if needed (assessed by the Principal Investigator or designee).

A subject is considered enrolled once consented. Screen failures are considered subjects who have consented, yet do not meet eligibility based on inclusion and/or exclusion criteria or withdraw consent prior to being randomized.

A subject can be randomized by mistake e.g., if the investigator realizes that the subject is not eligible after the subject has been randomized. If the subject has not started study treatment and has no data registered on endpoints the subject can be replaced by a new subject if the new subject can complete the investigation within timelines (before last subject last visit and within visit windows). A screen failure will be replaced under the same conditions.

Expected duration of the clinical investigation:

The investigation will be conducted from December 2022 through June 2023.

Endpoints & Assessments:

Primary Endpoint:

- Leakage through coupling registered at each bag change (yes/no).

Secondary endpoints:

- Product satisfaction evaluated at end of study by a question on a 4-point scale
- Preference evaluated at end of study by the question "Would you consider using the new coupling in the future? (Yes/No)"

Exploratory endpoint

Assessments

- Level of leakage at each bag change. If the subject responds as "yes"; the subject will be asked to grade the leakage on a 3-point scale.

Safety assessments:

- Adverse events
- Device deficiencies

Registered at the inclusion visit by Investigator or designee:

- Informed Consent
- Subject number
- Date of visit
- Check of inclusion criteria
- Check of exclusion criteria
- Current product (flat / concave, current bag size), item numbers (bag and baseplate)
- Name/type of randomized product

Baseline information and questions (registered at the inclusion visit by investigator or designee):

- Demographic (age, gender, height, weight)
- Stoma (age, type, cause, size, shape)
- For colostomy: Bristol stool scale
- Output frequency

Population/subjects

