1.3. Other Vendors

The data management system is delivered by [REDACTED]. The system is designed for electronic data capture, and it is compliant with the requirements of 21 CFR part 11.

The subject will be required to download and install a Patient Cloud app onto their smart phone. See section 11 for further details.

The app will be used to record subject diary responses.

In case of emergency, please contact the Clinical Manager from the above list of sponsor representatives.

2. Justification for conducting the clinical investigation

People with intestinal stomas have, despite development of better stoma products, problems with leakage induced peristomal skin complications which influence quality of life negatively^{1,2}. Although, the primary cause of peristomal skin complications is leakage of ostomy effluents under the adhesive barrier^{3,4}, leakage could also occur from other parts of stoma devices, for example through the coupling in 2-piece stoma devices. Coloplast wants to apply a new coupling system with improved functionality for SenSura Mio users who use a 2-piece appliance. The justification for conducting this clinical investigation is to investigate that the new coupling system is on par with the existing coupling SenSura Mio Click system with regards to leakage at the coupling.

3. Objective(s) of the clinical investigation

The aim of the study is to investigate how a new two-piece (2p) coupling system is evaluated by users in comparison with SenSura Mio Click.

The primary objective is to demonstrate that the performance of the new 2p coupling system is comparable to SenSura Mio Click coupling with regards to leakage at the coupling during wear in a clinical setting.

The secondary objective is to evaluate product satisfaction and preference of the new two-piece (2p) coupling system by users in a clinical setting.

4. Investigational Products

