5.3. Exploratory endpoint

5.4. Assessments

- Level of leakage at each bag change. If the subject responds as "yes" for the primary endpoint; the subject will be asked to grade the leakage on a 3-point scale.

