5.5. Safety Assessments

- Adverse events
- Device deficiencies

See appendix 2 for questions used as basis for the above endpoints and assessments.

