5.6. Rationale for selection and measurement of endpoints

The primary objective is to investigate the performance of a new 2p coupling in comparison with the SenSura Mio Click coupling with regards to leakage at the coupling during wear in a clinical setting. For this reason, leakage at the coupling is chosen as primary endpoint. The secondary endpoints will inform about the general satisfaction with the new coupling.

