5.10. Total expected duration of the clinical investigation

The dates below are approximate, and no subjects will be enrolled before all required approvals have been obtained. If changes are required, applicable regulatory authorities will be notified.

First subject enrolled (February 2023).

Last subject enrolled (April 2023).

Last subject completed (May/June 2023).

Final report (December 2023).

Subject participation will be approximately 42 days.

6. Clinical Investigation population

According to the sample size calculations (see section 10.2) 40 subjects are required to complete the study with measurements of the primary endpoint in both test periods. Considering a drop-out rate of 20%, the required total number of subjects to be enrolled in the trial shall be 50.

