The leakage (Y/N) per bag change will be analyzed by a repeated logistic regression model. The model will consider that observations corresponding to different subjects are independent, whereas observations corresponding to the same subject are correlated. The correlation between observations corresponding to the same product can be larger than observations corresponding to different products. Hence the model includes a fixed effect of product (SenSura Mio, test product), a fixed period effect, a random effect of subject and a random interaction effect of product and subject.

The marginal proportion of leakage for two products will be estimated and it will be tested if the odds ratio is significantly different from 1 on a 5% test level.

Analysis of the secondary endpoints

For preference, where the possible answer is "Yes" or "No", the proportion of subjects answering "Yes" will be calculated. By use of an exact test in the Binomial distribution a 95% confidence interval will be estimated for the proportion. Further, it will be tested if the proportion is significantly different from 50% when using a 5% test level. For questions answered on a 4-point scale the answers will be grouped in 2 (e.g., "Very satisfied" or "Satisfied", represented by "Yes" against "Very dissatisfied" and "Dissatisfied" represented by "No") and analysed using the method described above.

Analysis of the exploratory endpoint

[REDACTED]

[REDACTED]

[REDACTED]

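### The secondary endpoint labelled preference asks only about willingness to use the new coupling, so a significant Yes majority would not show preference over SenSura Mio Click

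*Combined protocol and SAP*

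**What the plan says.** The secondary objective in section 3 is "to evaluate product satisfaction and preference of the new two-piece (2p) coupling system". The overall aim in the same section is comparative: how users evaluate the new system relative to SenSura Mio Click.

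The synopsis and section 5.2 set the endpoint as "Preference evaluated at end of study by the question", followed by the item "Would you consider using the new coupling in the future? (Yes/No". Section 5.5 adds: "See appendix 2 for questions used as basis for the above endpoints and assessments". Appendix 2 shows the item with the same wording. The satisfaction item beside it also concerns the new coupling alone.

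For the analysis, section 10.0 calculates the proportion answering Yes with an exact 95% confidence interval, and "it will be tested if the proportion is significantly different from 50% when using a 5% test level". The same method is applied to the 4-point satisfaction item after it is reduced to two groups. Section 10.2 makes the level two-sided.

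The stated role of these endpoints is modest. Section 5.6 says: "The secondary endpoints will inform about the general satisfaction with the new coupling". The pass/fail criteria in section 10.3 mention leakage only.

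The content of the exploratory endpoint (section 5.3) and its analysis (section 10.0) are not visible in the public text, and three figures beside the final questions in Appendix 2 are not shown.

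**The concern.** Preference is a choice between alternatives, and this item offers one product. Willingness to consider the new coupling is compatible with three positions: preferring it, preferring SenSura Mio Click, or having no preference. A Yes therefore does not reveal which product the subject prefers.

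The 50% reference value adds to the risk of misreading. In a choice between two products, 50% is the point of no preference. For a yes/no item about one product, it marks only whether a majority says Yes. A reader who sees an endpoint called preference tested against 50% may take the first meaning when only the second applies.

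The report could then state a preference result that the question cannot give, and the preference part of the secondary objective would have no visible measure. The cross-over design makes this easy to avoid, since every subject is scheduled to wear both couplings and could be asked to choose between them.

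**Working it through.** **Inputs from the documents.** Section 6: "40 subjects are required to complete the study with measurements of the primary endpoint in both test periods". Section 10.1: 20% drop-out and 50 randomised. Sections 10.0 and 10.2: exact binomial test, null value 50%, two-sided 5%.

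**The plan's own figure.** 40 / (1 − 0.20) = 50, which matches the stated number randomised. No power statement for the preference item is visible.

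**What counts as significant.** The two-sided exact p-value for r Yes answers out of n, with r above n/2, is 2 × P(X ≥ r), where X is Binomial(n, 0.5).

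| Respondents | Yes | Share | p | Exact 95% CI |
|---|---|---|---|---|
| 40 | 26 | 65.0% | 0.081 | not needed |
| 40 | 27 | 67.5% | 2 × 0.01924 = 0.038 | 50.9% to 81.4% |
| 50 | 32 | 64.0% | 0.065 | not needed |
| 50 | 33 | 66.0% | 2 × 0.01642 = 0.033 | 51.2% to 78.8% |

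Both sizes are shown because analysis is on the ITT population and Appendix 2 also asks the items at study termination, so respondents could exceed 40. By symmetry, 13 or fewer Yes of 40 is also significant, in the other direction.

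**What 27 of 40 says about preference.** Suppose everyone who prefers the new coupling answers Yes. Then 27 Yes answers are compatible with any number from 0 to 27 of the 40 preferring it. This follows directly from the item not naming the comparator.

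**Illustration only.** The documents give no shares for preference or willingness, so these are assumed. Let q be the share who prefer the new coupling (all answering Yes) and w the share of the others who would also consider it. The Yes rate is y = q + (1 − q) × w. The chance of a significant Yes majority with 40 respondents is P(X ≥ 27), where X is Binomial(40, y).

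| q | w = 30% | w = 50% | w = 70% |
|---|---|---|---|
| 20% | y = 0.44: 0.2% | y = 0.60: 21% | y = 0.76: 92% |
| 30% | y = 0.51: 2.6% | y = 0.65: 44% | y = 0.79: 97% |
| 40% | y = 0.58: 15% | y = 0.70: 70% | y = 0.82: 99% |

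If only 90% of those who prefer it answer Yes, the q = 30% row becomes 1.0%, 29% and 92%. With q = 0 and w = 75%, y = 0.75 and the chance is 90%. In a two-option choice with a true 50:50 split, the same test favours the new coupling in 1.9% of trials.

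So the result can be significant when a minority, or nobody, prefers the new coupling. How likely that is depends entirely on w, which is unknown.

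**The case against.** **The question is printed in full wherever the endpoint is listed.** A careful reader can see what was asked, and section 10.0 promises only a Yes share, its interval and a test. The secondary objective speaks of preference of the new coupling without naming a comparator, and section 5.6 claims general satisfaction only. All of this stands and limits the weight of the point. It does not remove it: the aim in section 3 is comparative, preference ordinarily means a choice, and section 5.6 itself fits a willingness label better than a preference label.

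**A reader might infer that testing against 50% is an error.** The documents do not support that. A majority benchmark is coherent for a willingness item. Section 10.0 applies the same test to dichotomised satisfaction, which suggests a general majority rule, and nowhere calls 50% a no-preference point. The test can stay.

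**A reader might infer that the trial has no comparative preference question at all.** That cannot be concluded, because one could sit in the exploratory endpoint or in the figures that are not shown. It would not correct the label in the synopsis and section 5.2, but it would make an added question unnecessary.

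**The percentages in the illustration rest on assumed shares.** This is right. They show that the gap can be large, not how large it is in this trial.

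**Conclusion.** The point holds as one of labelling and interpretation. The endpoint called preference measures willingness to use the new coupling. A significant Yes result (27 or more of 40, or 33 or more of 50) supports the statement that more than half would consider using it, and no statement about preference over SenSura Mio Click. No visible item measures the preference named in the secondary objective.

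The size is limited. One secondary endpoint is affected in a study that section 10.0 calls exploratory. A reader might extend the point to the trial's main conclusion, but section 10.3 rests that on leakage alone.

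The conclusion depends only on the wording of the item and of the objective. The thresholds assume 40 or 50 respondents.

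Two neighbouring matters are separate and minor, and the point does not rest on them: the Appendix 2 instruction that places the final questions at visit 3, and the lack of a stated rule limiting new-coupling items to subjects who wore it.

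**What to change.** Rename the item as willingness to use the new coupling in the synopsis, section 5.2 and section 10.0. Keep the Yes share, the exact 95% interval and the 50% test, and describe the test as a majority benchmark.

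Then do one of the following.

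- **(a) Align the objective.** Change the word preference in the secondary objective (section 3) to match. The cost is wording only.
- **(b) Measure preference.** Unless a comparative item already exists in the content not visible here, add one Visit 4 question for subjects who wore both couplings: *Which coupling do you prefer: new / SenSura Mio Click / no preference*. Apply the exact 50% test among those stating a preference, and report the no-preference share and the results by sequence.

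Option (b) costs one app question and some power, because no-preference answers leave the test. At a true 75:25 split, power is P(X ≥ 27) = 90% with 40 stating a preference. With exactly 32 (20% of 40 having none), 23 are needed (p=0.020; 22 gives p=0.0501) and power is 74%. Part of that fall comes from the discreteness of the test at 32: if each of 40 subjects states a preference with probability 80%, power averages about 78%. The 75:25 split and the 20% are assumptions.

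Reporting by sequence is enough, and no period-adjusted test is needed. With no product preference and 75% favouring whichever product was worn last (assumed), the simple test rejects in 1.7% of trials with 20:20 stating a preference by sequence and in 4.9% with 24:16. It reaches 7.0% at 25:15, where all ten expected drop-outs fall in one sequence.

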5.3. Exploratory endpoint

5.4. Assessments

- Level of leakage at each bag change. If the subject responds as "yes" for the primary endpoint; the subject will be asked to grade the leakage on a 3-point scale.

5.5. Safety Assessments

- Adverse events
- Device deficiencies

See appendix 2 for questions used as basis for the above endpoints and assessments.

5.6. Rationale for selection and measurement of endpoints

The primary objective is to investigate the performance of a new 2p coupling in comparison with the SenSura Mio Click coupling with regards to leakage at the coupling during wear in a clinical setting. For this reason, leakage at the coupling is chosen as primary endpoint. The secondary endpoints will inform about the general satisfaction with the new coupling.

5.7. Demography and potential compromising factors

The subjects are not allowed to currently (upon inclusion) receive or have within the past 60 days received radio-and/or chemotherapy. However, low doses radio- and/or chemotherapy (assessed by Principal Investigator or designee) is allowed for indications other than cancer.

The subjects are not allowed to currently receive or have within the past 30 days received topical steroid treatment in the peristomal skin area, e.g., lotion or spray.

The subject shall use the test and comparator product as they normally would use their standard care product. Subjects are allowed to use all the accessories they normally use with their own product, such as paste, protection film, lotion, powder, and remover wipes/spray.

5.8. Randomisation Procedure

All subjects that meet the inclusion and exclusion criteria will be randomised to one of two treatment sequences. Both sequences examine the investigational product and the comparator investigational product. The two sequences are:

- First sequence: The investigational product, then the comparator investigational products.

- Second sequence: The comparator investigational product, then the investigational product.

Randomization will be centralized using [REDACTED]

5.9. Blinding

No blinding will be used in this investigation, as it is not possible to blind the products due to visible differences. The trial statistician will be blinded until database lock to ensure decisions related to data before database lock do not affect the final results.

5.10. Total expected duration of the clinical investigation

The dates below are approximate, and no subjects will be enrolled before all required approvals have been obtained. If changes are required, applicable regulatory authorities will be notified.

First subject enrolled (February 2023).

Last subject enrolled (April 2023).

Last subject completed (May/June 2023).

Final report (December 2023).

Subject participation will be approximately 42 days.

6. Clinical Investigation population

According to the sample size calculations (see section 10.2) 40 subjects are required to complete the study with measurements of the primary endpoint in both test periods. Considering a drop-out rate of 20%, the required total number of subjects to be enrolled in the trial shall be 50.

6.0. Eligibility criteria

To be included in the investigation, the subjects must comply with the selection criteria described below:

6.1. Inclusion criteria

To be included in the investigation a subject must comply with the following inclusion criteria:
1. Has given written consent to participate by signing the Informed Consent Signature Form
2. Be at least 18 years of age and have full legal capacity
3. Is able to handle (apply, remove, cut, etc.) the product and do the assessments themselves
4. Has an ileostomy or colostomy with consistent liquid fecal output (for colostomy: 6-7 Bristol stool scale*)
*See appendix 1
5. Currently use SenSura Mio Click 2p Click flat or concave with 50 mm coupling size
6. Have had their ostomy for at least 90 days
7. Be willing to change the bag at least twice per week
8. Is willing and suitable (determined by the Principal Investigator or designee) to use flat or concave 2p open product during the investigation
9. Is willing to use 2p maxi open bags during the investigation

6.2. Exclusion criteria

To be included in the investigation a subject must NOT meet the following exclusion criteria:

1. Is currently receiving or have within the past 60 days received radio-and/or chemotherapy
 - low doses radio- and/or chemotherapy (assessed by Principal Investigator) is allowed for indications other than cancer.
2. Is currently receiving or have within the past 30 days received topical steroid treatment in the peristomal skin area, e.g., lotion or spray
 - Low dose systemic steroid treatment (e.g., inhalation) assessed by the investigator are allowed.
 - Other systemic steroid treatment (e.g., injection or tablet) are not allowed.
3. Is pregnant and/or breast-feeding
4. Have a loop ileostomy
5. Is currently using convex baseplate
6. Has known hypersensitivity towards any of the products used in the investigation

6.3 Subject Recruitment & Screening

The recruitment of potential subjects will commence only when IRB approval is received. Recruitment will occur in the United States at the single-center [REDACTED]. The recruitment period from first subject enrolled to last subject enrolled will be approximately 3 months. The recruitment process will be conducted through site screening and advertisement.

If a subject is eligible and interested in participating, then written information about the investigation (subject information) will be sent to the subject to ensure they are given the opportunity to understand what the investigation is about. Subjects will be given plenty of time to have any questions they may have addressed by the investigator, or designee. The subject information provides information to subjects about how to contact the investigator or a representative thereof, or a representative of the sponsor (name, telephone number and e-mail address), if they wish to learn more about the study.

If an eligible subject is interested in participating after they have had time to review the subject information, a screening visit will be arranged. This visit will be done remotely to ensure privacy for the subject. When arranging the visit, the subject must have received the Information Form and given adequate time to review it. The subject will receive both written and verbal information about the possibility of allowing a companion to the remote visit and to any possible subsequent remote visits.

The subject has the right to wait before deciding to participate. If/when the subject decides to participate, he/she will be asked to sign the informed consent form. If a subject so desires, and it is certain that it is understood what the investigation entails, and the relevant forms have been signed, the subject is considered enrolled in the investigation.

The Coloplast clinical manager will have close contact to the site during the recruitment period. The principal investigator, or designee, will notify the clinical manager when a subject is enrolled and all future planned visits.

